- Lower Extremity Composite Percent Predicted: The percent predicted total force values will be determined based on reference equations adjusting for age, gender, height, and weight. The percent predicted force will be calculated for each side and the bilateral percent predicted values will be averaged for each lower extremity muscle group. The mean of the five averages in percent predicted scores will be calculated for each subject to create a percent predicted LEC score, and analyzed relative to baseline to create a UEC mean change in percent predicted score.
- Muscle strength (Total Force in kg)) for Each Individual Muscle Group: Bilateral total force for each individual muscle group included in the UEC and LEC will be reported.
- Percent of Predicted Muscle Strength in Each Individual Muscle Group: Bilateral percent predicted total force for each individual muscle group included in the UEC and LEC will be reported.
- Percent of Predicted Muscle Strength in the Knee Extensors: Percent predicted total force for the knee extensors will be reported.
- Total Score on the GNEM-FAS
- Self-Care Domain Score on the GNEM-FAS
- Individual Neuromuscular Quality of Life Questionnaire: A 45-item self-report questionnaire on the impact of key muscle disease symptoms on the ability to perform basic activities of daily

living, functional independence, relationships and overall well-being will be administered. Dimension scores and a Quality of Life score will be calculated.

- Clinical Global Impression Scale: Investigator assessment of severity of subject's GNEM using the CGI-improvement scale (CGI-I) during treatment, in 3 target areas.
- Creatine Kinase Levels: CK levels in serum will be measured to assess the degree of reduction of CK levels observed as a surrogate for muscle injury.

Drug Concentration Measurements:

- Serum Free Sialic Acid: Change in free serum SA level.
- Urine Sialic Acid - Free, Total and Bound: Changes from baseline in urine free, total and bound SA levels.

Urine Testing for ManNAc: Urine will be tested for the presence of ManNAc to detect compliance with prohibited medication restrictions.

Safety:

Safety will be evaluated by the incidence and frequency of AEs and SAEs, including clinically significant changes from baseline to scheduled time points in the following:

- Interval history
- Vital signs
- Physical examination results
- Clinical laboratory results
- Suicidal ideation and behavior
- Concomitant medications

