7.5.2.7 Individual Neuromuscular Quality of Life Questionnaire

The INQoL ([Vincent et al. 2007](#)), a tertiary endpoint, is an individualized self-report measure of health-related quality of life designed specifically for adults with muscle disease. The INQoL will be administered at the Baseline Visit and Weeks 8, 16, 24, 32, 40, and 48 (or Early Termination). The INQoL will be presented to the subject in paper format for completion prior to the administration of the performance tests. The INQoL is a 45-item measure consisting of ten subscales; four measure the impact of muscle disease symptoms, including weakness, locking (seizing), pain and fatigue of muscles. Five additional subscales evaluate the degree of symptom impact on particular areas of life, including activities, independence, social, emotional, and body image. The final domain assesses perceived and expected treatment effects and will not be administered due to the blinded nature of the study. All responses are given in a seven-point Likert scale, with higher scores indicating greater impact.

The INQoL will only be completed for subjects when a validated version of the scale is available in the subject's native language.

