#### 4.4 Tertiary Efficacy Endpoints

- Upper Extremity Composite Percent Predicted: The percent predicted total force values will be determined based on reference equations adjusting for age, gender, height, and weight. The percent predicted force will be calculated for each side and the bilateral percent predicted values will be averaged for each upper extremity muscle group. The mean of the four averages in percent predicted scores will be calculated for each subject to create a percent predicted UEC score, and analyzed relative to baseline to create a UEC mean change in percent predicted score.
- Lower Extremity Composite Percent Predicted: The percent predicted total force values will be determined based on reference equations adjusting for age, gender, height, and weight. The percent predicted force will be calculated for each side and the bilateral percent predicted values will be averaged for each lower extremity muscle group. The mean of the five averages in percent predicted scores will be calculated for each subject to create a percent predicted LEC score, and analyzed relative to baseline to create a LEC mean change in percent predicted score.
- Muscle strength (Total Force in kg)) for Each Individual Muscle Group: Bilateral total force for each individual muscle group included in the UEC and LEC will be reported.
- Percent Predicted in Each Individual Muscle Group: Bilateral total force for each individual muscle group included in the UEC and LEC.
- Percent of Predicted Muscle Strength in Each Individual Muscle Group: Bilateral percent predicted total force for each individual muscle group included in the UEC and LEC.
- Percent Predicted in knee extensors: Bilateral percent predicted total force of knee extensors.
- Total Score on the GNEM-FAS
- Self-Care Domain Score on the GNEM-FAS
- Individual Neuromuscular Quality of Life Questionnaire: A 45-item self-report questionnaire with 4 domains on the impact of key muscle disease symptoms on the ability to perform basic activities of daily living, functional independence, relationships and overall well-being will be administered. The individual domain scores will be calculated.
- Clinical Global Impression Scale: Investigator assessment of severity of subject's GNEM using the CGI-improvement scale (CGI-I) during treatment, in 3 target areas.
- Creatine Kinase Levels: CK levels in serum will be measured to assess the degree of reduction of CK levels observed as a surrogate for muscle injury.

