#### 5.4 Patient Reported Outcomes

- **GNEM Functional Activities Scale (GNEM-FAS) Total Score** will be calculated as the sum of the Total Scores range from 0 to 100 with higher scores representing greater independence with functional activities. Subscale scores will be calculated for the Mobility, Upper Extremity and Self-Care domains. Mobility subscale scores range from 0 to 40 with higher scores representing greater mobility. Upper Extremity subscale scores range from 0 to 32 with higher scores representing more skilled, independent use of the arms during functional activity performance. Self-Care subscale scores range from 0 to 28 with higher scores representing greater independence with functional care activities.
- **Individual Neuromuscular Quality of Life Scale (INQoL) Subscale and QoL:** The individual domain scores will be calculated using the scoring algorithms outlined in Appendix 10.5 Derived Variables.
- **Number of doses administered** will be calculated for each subject by summing the number of doses administered over all visits.
- **Prior medications** include all medications taken by the subject from 30 days prior to the signing of the informed consent until the first dose of study medication is administered.
- **Concomitant medications** include all medications that are taken after the first dose of study medication is administered.

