## SCORING OF DIMENSIONS:

Item Scaling	7-point Likert scale from 1 to 7 for items 1a, 2a, 3a, 4a 7-point Likert scales from 0 to 6 : for all other items
Weighting of items	Yes. Please see the scoring procedure below
Extension of the scoring scale	0-100
Scoring Procedure	
 
1. Weakness score = <math>(a+b+c) / 19 \times 100</math>
 
2. Muscle 'locking' score = <math>(a+b+c) / 19 \times 100</math>
 
3. Pain score = <math>(a+b+c) / 19 \times 100</math>
 
4. Fatigue score = <math>(a+b+c) / 19 \times 100</math>
 
5. Activities score = <math>[4 \times (AI+AII+AIII)] + [3 \times (BI+BII)] / 108 \times 100</math> 
If not working due to condition item → AIII=6
 
If retired/unemployed/work in home (not as a result of condition)
 
→ <math>[6 \times (AI+AII)] + [3 \times (BI+BII)] / 108 \times 100</math>
 
 
6. Independence score = <math>[12 \times A] + [3 \times (BI+BII)] / 108 \times 100</math>
 
7. Social relationships = <math>[3 \times (AI+AII+AIII+AIV)] + [BI+II+III+IV+V+VI] / 108 \times 100</math> 
If partner/spouse item (AI) not applicable:
 
→ <math>[4 \times (AII+AIII+AIV)] + [BI+II+III+IV+V+VI] / 108 \times 100</math>
 
 
8. Emotions score = <math>[3 \times (AI+AII+AIII+AIV)] + [3 \times (BI+BII)] / 108 \times 100</math>
 
9. Body Image score = <math>[12 \times (A)] + [3 \times (BI+BII)] / 108 \times 100</math>
 
10. Qol score: Add scores of items in section B for questions 5-9 (with correction i.e. 3X (BI + B2) for Quns 5,6,8&9 and BI+II+III+IV+V+VI for Qun 7), divide total score by 180 and multiply by 100 (to achieve percentage score)
 

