Interpretation and Analysis of missing data	
Quns 1-4
 
1A-4A If missing and rest of symptom qun missing (i.e. part B) → score zero
 
1B-4B a. If missing, score “1”
 
    b. If missing, impute previous value (part a)
 
    c. If missing, score “0”
 
Qun 5
 
5 A. If an item missing, sum completed items, and multiply by 6 if two items completed and 12 if only one item has been completed (to get score out of 72)
 
(N.B. “Work activities” item: if not working due to condition score “6” and count as a completed item).
 
EXAMPLE: If “Leisure activities” is missing, add values of “Daily activities” & “Work Activities”. Multiply this by 6.
 
    BI. If missing, impute average of completed “activities” items (from 5A)
 
    BII. If missing, score as “0”
 
Qun 6
 
6 A. if missing, score as “0”
 
    BI. If missing, impute value from 6A
 
    BII. If missing, score as “0”
 
Qun 7
 
7 A. If item missing, sum the completed items and multiply by 4 if three completed items, 6 if two completed items & 12 if one completed item
 
    BI. If missing, impute average of 7a items
 
        i) Relationship with spouse/partner &
 
        ii) Relationship with other family members
 
    BII. If missing, score as “0”
 
    BIII. If missing, impute value from “Friends” (7AII) item
 
    BIV. If missing, score as “0”
 
    BV. If missing, impute value from “Other people” (7AIV) item
 
    BVI. If missing, score as “0”

---	--

	
Qun 8
 
8 A. If item missing, sum the completed items and multiply by 4 if three completed items, 6 if two completed items and 12 if one completed item
 
BI. If missing, impute average of items completed in 8A
 
BII. If missing, score as “0”
 
Qun 9
 
A. If missing, score as “0”
 
BI. If missing, impute value from 9a
 
BII. If missing, score as “0”
 
Qun 10 (not included in this study)
 
10A I. If missing, score as “0”
 
II. If missing, score as “0”
 
III. If missing, score as “0”
 
10B I. If missing, score as “0”
 
II. If missing, score as “0”
 
III. If missing, score as “0”

--	--

(Vincent et al. 2007).

**Note:** Question #10 dealing with treatment effects was not administered or scored as part of this study due to the double-blind study design.

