Physical therapy – Hand-held Dynamometry (HHD)	Changes from baseline on Upper Extremity Composite and Lower Extremity Composite Percent Predicted: The percent predicted total force values will be determined based on reference equations adjusting for age, gender, height, and weight.	Tertiary efficacy analysis	Weeks 8, 16, 24, 32, 40, and 48	GEE Model
	Changes from baseline on actual and percent predicted in each Individual Muscle Group: Bilateral total force for each individual muscle group included in the UEC and LEC, and Percent Predicted of knee extensors.		Weeks 8, 16, 24, 32, 40, and 48	GEE Model
GNEM Functional Activities Scale (GNEM-FAS)	Changes from baseline on the total score on the GNEM-FAS	Tertiary efficacy analysis	Weeks 8, 16, 24, 32, 40, and 48	GEE Model
	Changes from baseline on the Self-Care Domain Score on the GNEM-FAS			
Individual Neuromuscular Quality of Life Questionnaire (INQoL)	Changes from baseline on the total score on a 45-item self-report questionnaire on the impact of key muscle disease symptoms on the ability to perform basic activities of daily living, functional independence, relationships and overall well-being	Tertiary efficacy analysis	Weeks 8, 16, 24, 32, 40, and 48	GEE Model
Clinical Global Impression scale (CGI)	The CGI-Severity scale (CGI-S), and improvement (CGI-I) during treatment	Tertiary efficacy analysis	Baseline (CGI-S only), Weeks 24 and 48	GEE Model
	The proportions of patients with reported degrees of change from baseline to week 48			Descriptive statistics
Creatine Kinase	Changes from baseline over time	Tertiary efficacy analysis	Weeks 8, 16, 24, 32, 40, and 48	GEE Model

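### The SAP summary table names an INQoL total score that is defined nowhere, and two of the questionnaire's missing-item rules produce wrong scores

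*SAP*

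**What the plan says.** **Which score is analysed.** The INQoL row of SAP 10.7 reads "Changes from baseline on the total score on a 45-item self-report questionnaire", with a GEE model at Weeks 8 to 48. Elsewhere the plan describes something different:

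- SAP 4.4: "The individual domain scores will be calculated".
- SAP 5.4, in an entry labelled for the subscales and QoL: "The individual domain scores will be calculated using the scoring algorithms outlined in Appendix 10.5".
- SAP 8.8.3 again refers to individual domain scores.
- The protocol synopsis: "Dimension scores and a Quality of Life score will be calculated". Protocol 7.6.4.3 speaks of subscale scores.

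Appendix 10.5 gives formulas for four symptom subscales, five life-domain subscales and one QoL score. It gives none for a total. The treatment-effects questions are left out. Protocol 7.5.2.7 says: "The final domain assesses perceived and expected treatment effects and will not be administered due to the blinded nature of the study".

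**How items are scaled.** Appendix 10.5 uses a "7-point Likert scale from 1 to 7" for 1a to 4a and "7-point Likert scales from 0 to 6" for all other items. All scores are stated to run from 0 to 100, and higher scores mean higher impact.

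**How blanks are handled.** In questions 1 to 4, the rule for a blank item b is "If missing, impute previous value (part a". A blank 6A or 9A is scored 0. Blank A items in questions 5, 7 and 8 are instead prorated from the A items that were answered.

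**The concern.** There are two separate problems.

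First, the table that sets out which analysis belongs to which endpoint names a score with no algorithm. A programmer would have to choose between nine subscales, the QoL score or an improvised sum. That choice should be made in writing before unblinding. The protocol does not settle it, because SAP section 1 gives the SAP precedence on analysis methods.

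Second, two imputation rules do not respect the scale they are applied to. One copies a value from a 1–7 item into a 0–6 item. The other treats a blank on the most heavily weighted item of a subscale as if the patient had reported no impact. A blank after baseline then looks like improvement, and a blank at baseline makes later visits look like worsening. INQoL is the trial's dedicated health-related quality-of-life questionnaire.

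**Working it through.** **Inputs, all from SAP Appendix 10.5.** Item a of questions 1–4 runs 1–7; every other item runs 0–6. Divisors are 19 (symptoms), 108 (life domains) and 180 (QoL). Independence and Body Image are each 12×A + 3×(BI + BII), divided by 108. I read each division as applying to the whole sum, which is what gives the stated 0–100 range.

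**The plan's own range, complete data.**

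- Symptom maximum: (7 + 6 + 6)/19 × 100 = 100.
- Independence or Body Image maximum: (12×6 + 3×12)/108 × 100 = (72 + 36)/108 × 100 = 100.
- QoL maximum: four questions at 3×12 = 36 give 144; question 7 adds 6×6 = 36; 180/180 × 100 = 100.

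The formulas are therefore sound when nothing is missing.

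**Item count.** Symptoms 4×3 = 12; life domains 5 + 3 + 10 + 6 + 3 = 27; treatment effects 3 + 3 = 6; total 45. Without the treatment-effects items, 39 are administered.

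**Rule (a): blank 1b–4b takes the value of a.** The score becomes (a + a + c)/19 × 100. There are 7 × 7 = 49 combinations of a and c.

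- The imputed b is 7, outside its 0–6 range, in the 7 combinations with a = 7.
- The score exceeds 100 only if 2a + c > 19. With a = 6 the most that can be reached is 18, so this needs a = 7 and c = 6: 20/19 × 100 = 105.3. That is 1 of 49.
- With b imputed as a − 1, or as a capped at 6, the maximum returns to (7 + 6 + 6)/19 × 100 = 100.

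**Rule (b): blank 6A or 9A scored 0.** If the lost answer was x, the subscale falls by 12x/108 × 100 = 11.1x points.

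| Lost answer | Fall in subscale (points) |
|---|---|
| 1 | 11.1 |
| 3 | 33.3 |
| 6 | 66.7 |

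With BI = BII = 6, the last row takes the score from 100 to 36/108 × 100 = 33.3.

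**Comparison with proration.** In question 5, complete A answers of 6, 6, 6 contribute 4×18 = 72. With one of them blank, the rule gives 6×(6 + 6) = 72. The contribution is 72/108 × 100 = 66.7 points either way, so a blank there costs nothing in this example.

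**The case against.** **On the total score.** A reader might infer that the SAP intends to sum 45 items, six of which are never collected. The documents do not support that: the item count describes the instrument, as it does elsewhere in both documents, and the omission is disclosed. Nor can it be said that INQoL results cannot be produced, since Appendix 10.5 gives a formula for every subscale and for QoL. The QoL instruction itself calls the sum it divides by 180 a total score, so QoL may be what 10.7 means. No passage says so, however, and 4.4 and 8.8.3 point to the domain scores. A wording mismatch remains.

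**On the blanks.** It would be too strong to say that missing items in questions 5, 7 and 8 are all scaled up. Only the A parts are; their blank BII-type items score 0 as well. Questions 6 and 9 have a single A item, so there is nothing to prorate from, which may explain the different rule. It does not make 0 a reasonable value for an item carrying two thirds of the subscale.

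**On the source.** The SAP attributes the scoring to the published questionnaire. Whether these rules follow it cannot be checked here. If they do, there is a fair case for keeping the published scoring available. A 7 on a 0–6 item is still out of range.

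**On size.** 105.3 and 66.7 are corner cases, and 66.7 concerns two of nine subscales. The documents give no frequency of blanks and no reason to expect them to differ between blinded arms. SAP 7.1 also sends missing data to Data Management for possible resolution before lock. All of this stands and limits the consequence.

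**Conclusion.** The point holds as a correction to a tertiary endpoint. SAP 10.7 names a score the SAP does not define and that its operative sections do not use. Rule (a) yields an invalid item whenever a = 7, although the score leaves the 0–100 range in only one combination. Rule (b) matters more: it shifts Independence or Body Image by 11.1 points per unit of the lost answer, 33.3 for a mid-scale answer and 66.7 at most. The shift is a false improvement if the blank is after baseline and a false worsening if it is at baseline.

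These are errors in individual scores. A reader might infer a biased treatment comparison, but that would depend on how often and in which arm items are left blank, which the documents do not say. SAP 8.8.3 reports nominal p-values without multiplicity adjustment for tertiary endpoints, so primary and key secondary conclusions do not depend on this.

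**What to change.** - In SAP 10.7, replace the total score with the nine subscale scores and the QoL score as defined in Appendix 10.5. This matches SAP 4.4 and 8.8.3 and the protocol synopsis. The QoL score should not displace the subscales, since 4.4 and 8.8.3 name the domain scores.
- In Appendix 10.5, keep an imputed 1b–4b within 0–6, either as a minus 1 or capped at 6. Choose one in advance.
- Set Independence or Body Image to missing when 6A or 9A is blank.
- Report the scoring as currently written as a sensitivity check, with the number of blanks by item, visit and arm.

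The cost is a few lines of SAP text and scoring code, a small departure from the cited scoring rules, and a few more missing subscale values. A blank 6A or 9A at baseline would remove that subject's change scores for the subscale. The a minus 1 mapping assumes the two response scales line up, which the documents do not show. Other rules that score a blank as 0 would remain. A blank BII in questions 5, 6, 8 or 9 can each move QoL by up to 3×6/180 × 100 = 10 points, and a wholly blank symptom question scores zero. The count of blanks would show whether these need attention.

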## 10.6 Adverse Events to Monitor

### 10.6.1 Gastrointestinal MedDRA Query

The following MedDRA PTs are included in the gastrointestinal SMQ version 17.1.

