5.2.4 Summary of Overall Risks and Potential Benefits

Since SA is a normal body compound with native pathways for degradative metabolism and rapid renal clearance, there is no evidence or expectation of a significant safety issue with SA replacement therapy. Data from nonclinical and clinical studies to date suggest SA-ER administered alone or with SA-IR does not pose any significant safety risks that can be identified at this time. Toxicology or adverse pharmacology findings were not observed in SA-treated animals; at very high doses, osmotic diarrhea may be observed in treated dogs.

In the 48-week Phase 2 study in 47 GNEM subjects, there were no deaths or other SAEs. The majority of subjects had TEAEs that were graded as mild to moderate severity. A single subject in the 3 g/day SA-ER group discontinued due to an AE of abnormal liver enzymes; the subject was subsequently identified as having a history of elevated liver function test results. The only AE experienced by a greater proportion of SA-ER treated subjects was abnormal liver function tests (5 subjects vs. 0 in the placebo group). It is likely alanine aminotransferase (ALT) elevations resulted from skeletal muscle disease rather than from liver damage, since gamma-glutamyl transpeptidase (GGT) was generally normal and serum CK was also elevated in these subjects. The time course of abnormality and lack of dose response suggest that these results are not study drug related. Sporadic abnormal levels of aspartate aminotransferase (AST) and ALT were also reported throughout the study, irrespective of time point or treatment group.

The most common treatment-related TEAEs were GI events (diarrhea, flatulence, abdominal pain and dyspepsia), headache and fatigue. The patterns of AEs were similar in the placebo-controlled phase of the study (the first 24 weeks) and for all 48 weeks. No correlation was observed between the GI events and free SA serum levels suggesting the frequency of GI events does not appear to be dose dependent. No subjects from the Placebo group reported diarrhea or abdominal pain, or had abnormal liver function tests after crossing over to SA-ER treatment in the continuation phase of the study.

Safety results in the ongoing Phase 2 study (UX001-CL202) indicate the most common TEAE reported by subjects receiving a higher dose of 12 g/day SA-ER/SA-IR involve GI disorders, including diarrhea, flatulence, dyspepsia, and abdominal pain.

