## 8.9 Safety Analyses

Analysis of safety will be performed on the safety analysis set. Blinded study data will be monitored on an ongoing basis by the clinical study team including the medical monitor and the clinical drug safety team to ensure patients' safety.

Safety will be evaluated by the incidence, frequency and severity of AEs and SAEs, including clinically significant changes from study baseline to scheduled time points in:

- Interval history
- Vital signs and weight
- Physical examination findings
- Clinical laboratory evaluations
- Suicidal ideation and behavior assessments
- Concomitant medications

All AEs will be coded using the Medical Dictionary for Regulatory Activities (MedDRA 17.1 or beyond). The incidence and frequency of treatment emergent AEs (occurred after the first dose of study drug) will be summarized by System Organ Class (SOC), Preferred Term (PT), severity, and relationship to treatment. The numbers (frequency) and incidence rates of AEs and SAEs will be summarized by treatment group. A by-subject listing will be provided

for those subjects who experience a SAE, including death, or experience an AE associated with early withdrawal from the study or study drug treatment. Each of these outputs will include tabulation by maximum severity for each SOC and preferred term. Summaries of AEs will be provided in descending order of frequency by SOC and preferred term.

Additional tables summarizing patient incidence (by preferred term) of the following will be generated:

- All AEs;
- SAEs;
- Treatment-related AEs;
- Treatment-related SAEs;
- AEs leading to the discontinuation of study drug or discontinuation of study;
- Deaths.

Separate outputs maybe be provided for subgroups defined by gender, and race (if feasible). Detailed listings for all AEs and listings and/or narratives will be provided for serious and significant AEs, deaths (with “on-study” deaths [deaths that occur before the end of safety follow-up period] identified).

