#### **8.9.1 Adverse Events to Monitor**

Appendix 10.6 includes certain adverse events and liver related investigations.

Tables summarizing patient incidence of the following will be generated:

- All AEs;
- SAEs;
- Treatment-related AEs;
- Treatment Related SAEs
- Liver-related Investigations

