#### Narrow Scope

Abdominal discomfort  
Abdominal distension  
Abdominal pain  
Abdominal pain lower  
Abdominal pain upper  
Abdominal symptom  
Abdominal tenderness  
Abnormal faeces  
Aerophagia  
Anorectal discomfort  
Bowel movement irregularity  
Change of bowel habit  
Constipation  
Defaecation urgency  
Diarrhoea  
Epigastric discomfort  
Eruption  
Faecal volume decreased  
Faecal volume increased  
Faeces hard  
Faeces soft  
Flatulence  
Frequent bowel movements  
Gastrointestinal pain  
Gastrointestinal sounds abnormal  
Gastrointestinal toxicity  
Infrequent bowel movements  
Nausea  
Non-cardiac chest pain  
Oesophageal discomfort  
Oesophageal pain  
Premenstrual cramps  
Vomiting

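### The SAP's list of monitored gastrointestinal terms leaves out dyspepsia, which the protocol names among the drug's common GI events, so the grouped GI incidence can be understated

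*SAP*

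**What the plan says.** SAP 8.9.1 (Adverse Events to Monitor) refers to the appendix for its terms: "Appendix 10.6 includes certain adverse events and liver related investigations". It then says "Tables summarizing patient incidence of the following will be generated", and lists all AEs, SAEs, treatment-related AEs, treatment-related SAEs and liver-related investigations.

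SAP 10.6.1 introduces the GI terms with "The following MedDRA PTs are included in the gastrointestinal SMQ version 17.1". A narrow-scope and a broad-scope list follow, both in alphabetical order.

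Protocol 5.2.4 describes the GI profile seen so far. For the 48-week Phase 2 study: "The most common treatment-related TEAEs were GI events (diarrhea, flatulence, abdominal pain and dyspepsia), headache and fatigue". For the extension study at 12 g/day, the most common treatment-emergent events "involve GI disorders, including diarrhea, flatulence, dyspepsia, and abdominal pain".

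Separately, SAP 8.9 provides general tables in which treatment-emergent AEs "will be summarized by System Organ Class (SOC), Preferred Term (PT), severity, and relationship to treatment".

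**The concern.** The tables in SAP 8.9.1 differ from the general tables in SAP 8.9 only through the term list, because 8.9 already asks for AEs, SAEs and treatment-related events over all terms. What the monitored GI category adds is one count per arm of subjects with at least one GI event of interest. A list that omits one of the four GI events named in the protocol's own safety summary does not fully do that job.

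GI tolerability matters in this programme. Protocol sections 5, 5.2.3 and 7.4.3 report more GI events at 12 g/day, and section 5 gives this as part of the benefit-risk reasoning for taking 6 g/day into Phase 3. A reader of the study report may well go to the grouped GI table first. If a reader later finds dyspepsia missing from it, adding the term after unblinding would look driven by the data.

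**Working it through.** The plan states no figure on this point, so there is none to reproduce. The check compares the two lists with the protocol, and then asks how much an omission of this kind could matter.

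**1. Terms named in Protocol 5.2.4 against SAP 10.6.1**

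| GI event named in Protocol 5.2.4 | Narrow list (33 terms) | Broad list (32 terms) |
|---|---|---|
| Diarrhoea | present | absent |
| Flatulence | present | absent |
| Abdominal pain | present | absent |
| Dyspepsia | absent | absent |

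Coverage is 3 of 4 named events. None of the 33 + 32 = 65 printed terms refers to dyspepsia or indigestion. In the narrow list the entry after Diarrhoea is "Epigastric discomfort". In the broad list Colonic lavage is followed by Dysphagia and Early satiety. SAP 8.9.1 does not say whether the tables use the narrow list, the broad list or both. That does not matter here, since dyspepsia is on neither.

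**2. Who is missed**

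The measure is patient incidence. A subject with dyspepsia and any other listed term is still counted. Only subjects with dyspepsia and no other listed term are lost. For an arm of n subjects, let d be the proportion with dyspepsia and o the share of those who also have another listed term:

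expected number missed = n × d × (1 − o)

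The documents give neither d nor o. With n = 40 (about 80 randomized 1:1) and assumed values of d from 5% to 15%:

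| d (assumed) | o = 0 | o = 0.5 | o = 1 |
|---|---|---|---|
| 5% | 2 | 1 | 0 |
| 10% | 4 | 2 | 0 |
| 15% | 6 | 3 | 0 |

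For example, 40 × 0.10 × (1 − 0.5) = 2 subjects, or 5 percentage points. Over these assumptions the range is 0 to 6 subjects in an arm (0 to 15 points). This is an illustration only, and it applies equally to either arm.

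**3. Effect on each arm's incidence and on the difference**

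Let m be the proportion of an arm with dyspepsia and no other listed term.

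- Within an arm: reported GI incidence = GI incidence with dyspepsia included − m. As m cannot be negative, the reported figure is too low or unchanged.
- Between arms: reported difference = difference with dyspepsia included − (m on SA-ER − m on placebo). The sign of the bracket is not known. If m is larger on SA-ER the difference shrinks, if m is larger on placebo it grows, and if the two are equal it is unaffected.

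**The case against.** **Dyspepsia is reported elsewhere.** This stands. SAP 8.9 tabulates treatment-emergent AEs by system organ class and preferred term, by treatment group, with further preferred-term tables for SAEs and treatment-related events. Protocol 5.2.4 groups dyspepsia with GI disorders, so the organ-class row should also give a GI total that includes it. No information is lost from the safety report. What remains is that the category the SAP sets apart for monitoring omits a GI event the protocol names.

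**The list is a standard query, and the printed text may be faulty.** This stands in part. The SAP attributes the list to a MedDRA query, version 17.1, but identifies it only as gastrointestinal, and the query's contents cannot be seen from the documents. If the query contains dyspepsia and the tables are programmed from the query, only the printed list is wrong. The entry Eruption, which is not obviously a GI term, suggests that a copying or text-reading error is possible close to where Dyspepsia would fall. Alphabetical order without a visible gap is weak evidence against a lost line. Each possibility calls for the same check. If the query does not contain the term, the list needs a supplement or a stated reason for leaving it out.

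**Neighbouring terms would catch it.** This cannot be relied on. Epigastric discomfort and upper abdominal pain are separate preferred terms, and Protocol 5.2.4 itself reports dyspepsia apart from abdominal pain.

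**Stronger readings that the documents do not support.** A reader might infer that the omission biases the GI comparison in favour of SA-ER. That would need more dyspepsia-only subjects on SA-ER than on placebo. No rate by arm is given, and for Phase 2 Protocol 5.2.4 says that abnormal liver function tests were the only AE seen in a larger proportion of SA-ER subjects. It also says that GI event frequency did not appear dose dependent. A reader might also object to listed terms with no stated link to this drug, such as Pernicious anaemia or Premenstrual cramps, or want a redesigned main GI table. Those are matters of preference, since the SAP attributes the terms to the query.

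**Conclusion.** The point holds as a gap between the two documents. In the text available, dyspepsia is on neither list in SAP 10.6.1, although Protocol 5.2.4 names it twice among the drug's common GI events. The grouped GI patient incidence can therefore be understated for subjects whose only GI event is dyspepsia.

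It does not follow that the incidence will be understated. The size is unknown and could be zero. The range of 0 to 6 subjects per arm of 40 rests on assumed dyspepsia rates of 5% to 15% and on any degree of overlap from none to complete. No direction can be given for the arm difference.

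Two assumptions remain: that the tables will be programmed from the list as printed, and that the list in the source PDF matches the text read here. Efficacy conclusions and type I error are untouched, and the stopping rules in Protocol 7.3.3.1 do not use this list. This is a minor correction to a descriptive safety table.

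**What to change.** Before unblinding:

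1. Check the printed lists in SAP 10.6.1 against the source query, and state the exact name and version of that query.
2. Add Dyspepsia to the monitored GI terms, which makes 66 terms and covers 4 of the 4 GI events named in Protocol 5.2.4. If the query does not contain the term, label it as sponsor-added and reword the introductory sentence of 10.6.1 so that the extended list is not presented as the query itself.
3. Check the narrow-scope entry Eruption as a possible transcription error, and correct it if the source differs.

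The cost is a small edit to a SAP appendix and the matching change in the table programs. No new data are needed, and neither the efficacy analysis nor the conduct of the trial changes.
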